### 9.3.3. Exposure

#### Study drugs

The main drug of interest in both the effectiveness of RMM as well as safety study is Strontium ranelate (ATC M05BX03).

The safety will be compared with users of oral bisphosphonates (active comparator) (ATC M05BA04 – alendronate, M05BA06 - ibandronate, or M05BA07 - risedronate)

While a number of the databases contain information on drug dispensing, for ease of description we refer to data as relating to "prescriptions" throughout the protocol.

#### Duration of treatment

In order to create episodes of drug use the duration of treatment will be calculated using the following definitions:

- *Legend duration*: Total units /prescribed daily dose.
- *Normal duration*: Total number of defined daily doses (DDD) prescribed: Total Units\*Strength)/DDD value.

In order to define periods of continuous use of study drugs, any two prescriptions of the same drug will be concatenated if the gap between the end of the first of the two prescriptions and the start of the second of the two prescriptions was less than 30 days apart, a carry-over period of 30 days will be added after last prescription to account for lack of compliance and carry-over effects.

#### Exposure categorization for safety studies

For the incidence rate calculations the period of drug use will be divided in mutual exclusive periods of a month to be able to investigate the rate of cardiac events during current, recent or past use. The period 0-180 days after cessation of study drugs use will be classified as recent use and the period 181 days or more will be classified as past use. If patients switch from SR to BP or vice versa, they will contribute to the respective exposure category.

For the case control study we follow the same categorization. A patient will be classified as current user if the last prescription is ongoing or stopped less than 30 days ago before the index date. Patients will be classified as recent users if last prescription stopped between 30 and 180 days before the index date. Patients are past users if the last prescription for a study drug stopped more than 180 days before index date.

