#### 9.2.6.2. Safety study

Patients will be followed from the date of incident prescription of strontium ranelate or oral bisphosphonate (after one year of non-use) which follows the latest of the following dates:

- Start of study period.
- One year of valid data in database.

Until the earliest date of:

- The end of enrolment in the database (due to moving out or death).
- Date of last data capturing in the database.

The safety study will be performed in two periods (up till May 2013 and from June 2013 onwards) based on the date of cohort entry.

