#### ***Utilization patterns patient level***

For patient level analyses SR users will be divided into incident and prevalent users. Incident users are all persons who have a first prescription for SR during the study period (one year of absence prior), prevalent users are persons who have at their first prescription during the analysis period evidence of prior prescriptions in the year before the start of the period. For prevalent users we do not know how long they have been using SR.

*Persistence of use:* persistence is the time since start of SR to the time of stopping or switching. Persistence will be calculated only for incident users.

*Stopping:* stopping is defined as lack of SR treatment within a gap of 30 days after the end of the last prescription in the treatment episode. Stopping will be calculated only for incident users.

*Switching:* switching is defined as stopping SR treatment and start of another osteoporosis treatment, during use or within a gap of 30 days after stopping. Switching will be assessed both for incident as well as prevalent users.

The gap period will be varied to 0 and to 90 days to look at the impact of the choice of gap period on these variables. Kaplan Meier models will be used to estimate persistence of use.

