### 9.7.3.3. Relative risks

Using a matched case control approach we will use conditional logistic regression to estimate the association with the occurrence of endpoints and between current use of SR and 1) past use of study drugs; 2) current use of bisphosphonates. Control for confounding will be based on the change in estimate method as proposed by Greenland *et al* (1993). All analyses will be stratified by period. We will primarily consider factors measured at baseline, and only for those at index date for which we are sure they cannot be an intermediate between drug exposure and outcome.

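### The past-use reference for current SR is defined by SR and three oral bisphosphonates only, so it may contain an unknown share of patients currently on another osteoporosis drug

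*Protocol*

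**What the plan says.** Section 9.3.3 (Study drugs) names SR as the drug of interest and three oral bisphosphonates as comparator: "M05BA04 – alendronate, M05BA06 - ibandronate, or M05BA07 - risedronate". For the case-control study, current use runs to 30 days after the last prescription ends and recent use to 180 days. After that, "Patients are past users if the last prescription for a study drug stopped more than 180 days before index date". The only rule for a change of drug is "If patients switch from SR to BP or vice versa, they will contribute to the respective exposure category".

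Section 9.2.6.2 ends safety follow-up at the end of enrolment or at last data capture. Starting another osteoporosis drug does not end it.

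Section 9.7.3.3 estimates the association with each endpoint "between current use of SR and 1) past use of study drugs; 2) current use of bisphosphonates". The abstract gives the same two contrasts.

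Section 9.7.2.1, on utilization, takes a wider view of treatment: "switching is defined as stopping SR treatment and start of another osteoporosis treatment, during use or within a gap of 30 days after stopping".

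**The concern.** The utilization part expects patients to leave SR for some other osteoporosis treatment. The safety part recognises only moves between SR and the three oral bisphosphonates, so a patient who moves to anything else drifts into past use while still being treated.

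Other parts of the protocol suggest that such patients exist in some number:
- Section 7.2 reports that the 2014 label restricts SR to patients for whom other osteoporosis products are not possible.
- Section 6 says Italian GPs can neither start nor renew SR since December 2013. Italy supplied 1,209 of the 5,819 incident users counted for 2012 (section 9.5).
- Section 9.5.1 cites 40.4% to 47.9% second-line use of SR. That many of these patients' next drug is not an oral bisphosphonate is a plausible inference, not something the protocol states.

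At stake is how the first contrast is read. If the reference mixes treated and untreated patients, in proportions that may shift after each safety communication, its odds ratio has no clear meaning and may not be comparable between the two periods.

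**Working it through.** **1. Trace one patient through the rules.** SR supply ends on 30 June 2013 and a non-study osteoporosis drug starts in July. Under 9.7.2.1 this is a switch, since it falls within 30 days. Under 9.3.3 the patient is recent until day 180 (27 December 2013) and a past user from 28 December 2013, on the other drug throughout. Under 9.2.6.2 follow-up continues. Nothing removes or marks this patient.

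**2. Check the only candidate safeguard.** Section 9.3.4 lists use of any ATC M05B drug in the year before cohort entry or index date.
- Measured at cohort entry, it precedes any later switch; 9.7.3.3 relies primarily on baseline values.
- Measured at index date, it includes the study drugs themselves (M05BX03, M05BA04/06/07). It is then positive for practically all current users, and for past users who stopped 181 to 365 days earlier, so it cannot isolate other-drug use.
- Under 9.9 it is retained only if it changes the estimate by 10%.

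The sensitivity analyses in 9.7.5 cover the gap period, the risk window and the exclusion of Spain. None touches this.

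**3. The plan's own figure.** Section 9.5.2 gives 415 myocardial infarction cases for an odds ratio of 1.5 with 90% power, 20% SR use in controls and 1:10 matching. Case exposure is 1.5 × 0.2 / (1 + 0.2 × 0.5) = 0.2727. Taking alpha 0.05 as two-sided, standard formulas give 385 (two proportions), 400 (with continuity correction), 419 (Dupont's matched formula, exposure correlation 0.2) and 426 (unpooled variance). The figure is reproducible and is not in dispute.

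**4. Size of the effect on the first contrast.** Let f be the share of past users on another osteoporosis drug and r their event risk relative to untreated past users. Assume no current SR user also takes such a drug. The reference risk is then multiplied by (1 − f + f × r), so

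observed OR = 1.5 / (1 − f + f × r).

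The protocol gives neither f nor r. The assumed ranges are f from 10% to 50% and r from 0.7 to 1.5:

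| r | f = 10% | f = 30% | f = 50% |
|---|---|---|---|
| 0.7 | 1.55 | 1.65 | 1.76 |
| 0.8 | 1.53 | 1.60 | 1.67 |
| 1.0 | 1.50 | 1.50 | 1.50 |
| 1.25 | 1.46 | 1.40 | 1.33 |
| 1.5 | 1.43 | 1.30 | 1.20 |

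For example, f = 0.5 and r = 1.5 gives 1.5 / 1.25 = 1.20; f = 0.5 and r = 0.7 gives 1.5 / 0.85 = 1.76.

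**5. Power, as illustration only.** With 415 cases the two-proportion formula gives 0.92 at an odds ratio of 1.5. At f = 30% this falls to 0.79 for r = 1.25 and to 0.59 for r = 1.5. The calculation keeps the plan's 20% SR use among all controls, so it is not a power figure for the past-use contrast itself.

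**The case against.** Four arguments carry weight.

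**The category does what its label says.** The protocol calls the group past use of study drugs and never calls it unexposed or untreated. A reader might infer that the protocol contradicts itself, or that SR is being measured against a treated group. Neither is supported: the rule is applied as named, and the group is a mix whose treated share is unknown.

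**The comparison that answers the objective is not affected by this reference.** Safety objective 2 compares SR with oral bisphosphonates, which is the second contrast in 9.7.3.3. A reader might extend the bias to it, but that contrast does not use past users. This limits the point but does not remove it, because the past-use contrast is listed first in 9.7.3.3, repeated in the abstract and will be reported.

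**The share could be small.** Section 9.5.2 expects 25,128 SR and 125,640 BP starters, so SR starters are 25,128 / 150,768 = 16.7% of the cohort. If past users divide in the same way and half the past SR users have moved to other drugs, f is 8.3%, and at r = 1.5 the odds ratio reads 1.5 / 1.0417 = 1.44. Matching on index date and stratification by period also limit distortion over calendar time. This stands as a plausible low scenario. It is not an upper bound, because BP starters can also move to non-study drugs.

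**It could be left to the analysis plan.** Section 9.7 defers detail to a later document. However, the protocol has not left the matter open: 9.3.3 fixes the definition of past use, and that definition admits these patients.

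**Conclusion.** The point holds for the first contrast only. The past-use definition admits patients currently on non-study osteoporosis drugs, and no censoring rule, covariate or sensitivity analysis in the protocol separates them.

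Size and direction cannot be computed from the protocol. Under the assumed 10-50% share and risk ratio of 0.7-1.5, a true odds ratio of 1.5 reads about 1.20 to 1.76. At a risk ratio of 1 it reads 1.50 whatever the share. A reader might infer that the SR effect is necessarily diluted, but a risk ratio below 1 inflates it. Bias arises only if the other drugs, or the reasons for receiving them, change event risk.

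This is a worthwhile and inexpensive improvement to a planned contrast. It does not invalidate the safety study.

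**What to change.** In section 9.3.3:
- List the non-study osteoporosis drugs by code. Section 9.7.2.1 gives no list, and Appendix 14.3.1 covers only SR and the bisphosphonates.
- Extract them for both SR and BP starters. Section 9.7.2.1 assesses switching for SR users only.
- Add a time-varying category for current or recent use of another osteoporosis drug, and keep it out of the past-use reference.
- Report the estimate under the protocol's present definition of past use as a sensitivity analysis.

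The work is a code list, one further drug extraction and one exposure category. There are two real costs. The past-use group becomes smaller and more selected on having stopped all treatment, which brings its own differences in frailty and adherence; the sensitivity analysis shows how much this matters. And the table in section 9.4 marks specialist prescriptions as incomplete in four of the five databases (all but Aarhus), so some use of other drugs will remain unseen.

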#### 9.3.4. Co-variables (potential confounders)

All potential confounders listed here will be identified both at cohort entry (for characteristics of new SR users and BP users -See [Section 9.7.3.1](#)) and at index date for cases & controls within the safety study (See [Section 9.7.3.3](#)).

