### 7.2. Regulatory action

In the frame of 13th PSUR assessment, data submitted raised concern regarding cardiovascular safety beyond the already recognized risk for venous thromboembolism. Analysis of pooled data from randomized studies in around 7,500 post-menopausal women with osteoporosis showed an increased risk of myocardial infarction with Protelos/Osseor as compared with placebo (1.7% versus 1.1 %), with a relative risk of 1.6 (95% CI, 1.07 to 2.38), and an increased risk of venous thrombotic and embolic events — 1.9% versus 1.3 % with a relative risk of 1.5 (95% CI, 1.04 to 2.19).

As a result of this assessment, an increased risk for serious cardiac disorders, including myocardial infarction has been identified and risk minimization measures specifically targeting this identified risk were recommended by the CHMP. These risk minimization measures included a restriction of the target population by excluding patients with established, current or past history of ischaemic heart disease, peripheral arterial disease and/or cerebrovascular disease and/or uncontrolled hypertension, and restricting the indication to severe osteoporosis in postmenopausal women at high risk for fracture to reduce the risk of vertebral and hip fractures and the treatment of severe osteoporosis in adult men at increased risk of fracture. Patients with significant risk factors for cardiovascular events (e.g. hypertension, hyperlipidaemia, diabetes mellitus and smoking) should only be treated with strontium ranelate after careful consideration. In addition, strontium ranelate therapy should only be initiated by a physician with experience in the treatment of osteoporosis. These changes were disseminated in the form of a DHPC in May 2013.

In view of this newly identified risk of serious cardiac disorders, an overall benefit/risk review under Article 20 of regulation (EC) No 726/2004 started in May 2013 and was finalized on 20 February 2014 ([EMA/112925/2014, 2014](#)). This led to a restriction of the indication to patients (postmenopausal women and men) with severe osteoporosis at high risk of fracture for whom treatment with other medicinal products approved for the treatment of osteoporosis is not possible due to, for example, contraindications or intolerance. As part of RMM, a new DHPC was disseminated in March 2014.

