#### NEW INDICATIONS OF USE

Regarding the new restrictions, some of these criteria are not directly captured in the databases. Thus, operational definitions are proposed using some proxies which could lead to some misclassification or underestimation of the new restrictions. Therefore, some validation or refinement steps based on data availability and quality are required and will be further discussed with each of the academic partners before data extraction; for instance through feasibility assessed on a random sample.

- *A physician with experience in the treatment of osteoporosis.* The operational definition for this in our data sources will be:
  - Therapy initiation in secondary care settings (where available: Aarhus Database)OR
  - Therapy initiation in primary care by a physician with a “high number” of patients diagnosed with osteoporosis or on anti-osteoporosis treatment under his/her care. As both national regulations and prescribing practices have changed throughout the participating databases in recent months (e.g. general practitioners are not allowed to either initiate or prescribe repeat prescriptions of SR in Italy, different to Spain, where GPs cannot initiate but can issue repeat prescriptions of the drug), the definition of “high number” of patients with a diagnosis or treatment for osteoporosis will be based on national figures: a GP will be classified as “experienced” (with a high number of osteoporotic patients) if the number of patients with a diagnosis or treatment for osteoporosis registered with him/her is above a discriminant threshold; for instance, in the top quartile (percentile 75 or above) in the same country/data source.
- *Initiation of SR therapy not in first line,* will be operationalized as:
  - Previous use of other anti-osteoporosis drugs at any time before SR therapyOR
  - History of any formal contra-indications or precautions for the use of oral bisphosphonates (according to SmPC for alendronic, risedronic and ibandronic acid) not recognised as contra-indications or precautions for the use of SR [Appendix 14.3] at any time before SR therapy.

- Use of SR for the treatment of severe osteoporosis, will be operationalized as:
  - History of a previous osteoporotic fracture [Appendix 14.3.2] (at any time before SR therapy initiation).
- OR

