##### *General potential confounders*

- Age (matching factor).
- Gender (matching factor).
- Calendar time (matching factor).
- Alcohol abuse (if available).
- Health seeking behaviour: number of visits to general practitioner or hospital contacts in the year before cohort entry/index date.
- Use of any drugs: number of different compounds used in the year previous to cohort entry/index date.

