## Confounding

Due to the observational design chosen, causality in the observed associations will not be established. Instead, associations between drug use and risks will be assessed. As confounding by indication (with SR patients most likely to suffer more severe osteoporosis) will likely produce differences between SR and bisphosphonate users, especially after the different DHPCs, we will use several methods to deal with between-person confounding:

1. Restriction: comparative studies will be conducted only in persons without contra-indications to restrict the population to those that would be prescribed SR according to the new label.
2. Matching: for the comparative studies we will match cases to controls on age, sex, date, country.
3. Adjustments: we will adjust for all co-variables that are associated with a 10% change in the primary risk estimate.

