### Contraindications / precautions of use of oral bisphosphonates (and not mentioned in the SR SmPC)

Term/Description	ICD10	ICD9CM	Read codes	ICPC
Achalasia	K22.0	530.0	J100.	No code
Balloon dilatation of achalasia			X20Ud	No code
Oesophageal obstruction/stricture/stenosis	K22.2 K31.1 K31.2	530.3	XaB59 J103z XE0aM XaB8i J103z	D84.05 (oesophageal stenosis)
Barrett's esophagus	K22.7	530.85	Xa9Bz X3007	No code
Oesophagitis/Esophagitis	K20	530.1	J101. J101z Xa1q7 X3009	D84.03 (oesophageal reflux with oesophagitis)
Gastro-esophageal reflux disease	K21	530.81	XE0aL XE0aO X3003	D84.00 (oesophageal reflux without oesophagitis)
Esophagic ulcer/perforation/hemorrhage	K22.1 K22.3	530.2 530.4 530.82	J102. J102z	No code
Gastric/duodenal/jejunal/peptic ulcer	K25 K26 K27 K28	531 532 533 534	XE0aP XE0aQ J11y. J11yz	D85.00 D86.00 D86.01
Gastro-intestinal hemorrhage/bleeding	K92.0 K92.1 K92.2 I85.0 I98.21	530.7 530.82 578 456.0 456.1 456.20	J68.. XE0bJ J68zz G850. G8520 XM1RR* XaB3K	D14.00 (haematemesis) D15.00 (melaena) D16.00 (rectal bleeding)
Dysphagia	R13	787.2		D21.00
Diverticulum of oesophagus	K22.5 Q39.6	530.6	PA42. PA45. J106. J106z	D84.01
Gastritis/Duodenitis	K29	535	X301N J155. J15.. J15z. J156. J153. Jyu13 XE2bH J4000 X302J	D87.01

Esophageal surgery	0D11	42	7608.	No code
	0D12		Xa7yZ	
	0D13		X20Tp	
	0D15		Xa3lm	
	0D51		760..	
	0D52		XaB2P	
	0D53			
	0D54			
	0D55			
	0D71			
	0D72			
	0D73			
	0D74			
	0D75			
	0D84			
	0D87			
	0DB1			
	0DB2			
	0DB3			
	0DB4			
	0DB5			
	0DB7			
	0DF5			
	0DH5			
	0DL1			
	0DL2			
	0DL3			
	0DL4			
	0DL5			
	0DM5			
	0DP5			
Hypocalcemia	E83.5	275.41	X40QW	No code

\* "History of". Not to be used for incident diagnoses.

**NOTE:** No codes are available in any of these coding languages for atypical femoral fracture, which is recognized as a precaution of use in the oral bisphosphonates SmPC.

---

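### The confounder list for the SR versus bisphosphonate comparison omits contraindications and precautions to oral bisphosphonates, a reason for SR use that the protocol itself names and codes

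*Protocol*

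**What the plan says.** - **Reason for choosing SR.** Section 7.2 says the review finalised in February 2014, communicated in March 2014, limited SR to severe osteoporosis in patients "for whom treatment with other medicinal products approved for the treatment of osteoporosis is not possible due to, for example, contraindications or intolerance".
- **Operational definition.** Section 9.3.2, for the risk-minimisation study, counts SR as not first line if there was earlier use of another osteoporosis drug, or "History of any formal contra-indications or precautions for the use of oral bisphosphonates" at any time before SR.
- **Codes.** Appendix 14.3.2 gives a code list for these conditions: oesophageal disease and surgery, reflux, ulcer, gastro-intestinal bleeding, dysphagia, gastritis and hypocalcaemia. It stands apart from the appendix table of covariates.
- **Confounders.** Section 9.3.4 opens with "All potential confounders listed here will be identified both at cohort entry" and also at the index date of cases and controls. Its three groups (general, cardiovascular, osteoporosis/fracture) contain none of these conditions.
- **Control of confounding.** Section 9.7.3.3 uses change-in-estimate selection, and section 9.9 sets the threshold at 10%. Section 9.9 describes the channelling as one of severity: "As confounding by indication (with SR patients most likely to suffer more severe osteoporosis) will likely produce differences between SR and bisphosphonate users".

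**The concern.** In an active-comparator study, the recorded reason for giving one drug rather than the other is a leading candidate confounder. From 2014 the label steers towards SR those patients who cannot take other osteoporosis drugs, and the comparator is a class that the coded conditions argue against. Some imbalance in these conditions between SR and BP starters is therefore to be expected. If they also relate to myocardial infarction, venous thromboembolism or cardiovascular death, the odds ratio for current SR against current BP would carry part of that relation. This comparison, before and from June 2013, is a stated primary safety objective (section 8). A variable that is not on the list cannot be picked up by a selection step that works from the list.

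**Working it through.** **1. Does any planned step address these conditions?**

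| Step | Where | What it covers | BP contraindications? |
|---|---|---|---|
| Restriction | 9.2.5.3 | ischaemic heart, peripheral arterial and cerebrovascular disease, uncontrolled hypertension, Paget's disease; prior VTE for the VTE outcome | No |
| Matching | 9.3.1 | birth year, gender, index date, data source | No |
| Adjustment | 9.3.4, 9.7.3.3, 9.9 | listed co-variables that change the estimate by 10% | Not listed |
| Cohort description | 9.7.3.1 | all contra-indications, which by context are those to SR | Descriptive only |

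The nearest listed variables are antiplatelet and anticoagulant use in the prior year, prior osteoporosis drugs in the prior year, number of visits, and "Use of any drugs: number of different compounds used in the year previous to cohort entry/index date". Each is a partial proxy. None records an upper gastro-intestinal condition or hypocalcaemia.

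**2. Which patients are affected?** Section 9.5.2 expects at least 30,000 SR starters in 2004–2012 out of 31,500 to 33,000.

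- 30,000 / 33,000 = 91%; 30,000 / 31,500 = 95%.
- The remainder, 500 to 1,000 a year over 2013–2015, is 1,500 to 3,000 starters. Only those after March 2014 fall under the quoted label reason.

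All relative-risk analyses are stratified by period (section 9.7.3.3), so the large earlier group does not dilute the later stratum. It does mean that most SR starters predate the label reason.

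**3. How large could the bias be?** The documents give neither the prevalence of these conditions by drug nor their relation to the endpoints, so every input here is an assumption. With prevalence p in each group and outcome risk ratio RR,

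bias factor = [1 + p_SR(RR − 1)] / [1 + p_BP(RR − 1)].

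| p_SR | p_BP | RR | Calculation | Factor |
|---|---|---|---|---|
| 0.40 | 0.15 | 1.2 | 1.08 / 1.03 | 1.049 |
| 0.40 | 0.15 | 1.3 | 1.12 / 1.045 | 1.072 |
| 0.40 | 0.15 | 1.5 | 1.20 / 1.075 | 1.116 |
| 0.30 | 0.20 | 1.3 | 1.09 / 1.06 | 1.028 |
| 0.30 | 0.20 | 1.5 | 1.15 / 1.10 | 1.045 |

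The inflation is about 3% to 12%, and only one of the five scenarios passes the protocol's 10% criterion. A wider assumed grid (20% to 50% in SR, 10% in BP, RR 1.2 to 2.0) runs from 1.04 / 1.02 = 1.02 to 1.50 / 1.10 = 1.36. All of these factors suppose that the listed covariates absorb nothing.

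**4. How does that compare with precision in the later stratum?** Using section 9.5.2's own inputs, the share left after exclusions is 0.9 × (1 − 0.192) + 0.1 × (1 − 0.295) = 0.798. At 0.19 per 100 person-years over 2 years, the expected infarctions among 2013–2015 SR starters are:

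- 1,500 × 0.798 × 0.0038 = 4.5
- 3,000 × 0.798 × 0.0038 = 9.1

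With 9 exposed cases the standard error of the log odds ratio is at least √(1/9) = 0.33, so each 95% limit lies at least exp(1.96 × 0.33) = 1.9-fold from the estimate. The protocol gives no forecast of starters after 2015 and no rates for the other two endpoints.

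**The case against.** The strongest reply is that the best-known pathway is already covered. If ulcer or bleeding history matters because antiplatelet or anticoagulant treatment is withheld, section 9.3.4 lists low-dose aspirin, clopidogrel and the anticoagulant classes, along with smoking, alcohol abuse, kidney disease, drug count and visits. Much of this stands. A reader might infer that the later odds ratio carries confounding that nothing in the plan can remove; the documents do not support that, because these proxies may remove part of it. What remains is that use over one year cannot tell a patient with no need of the drug from one in whom bleeding ruled it out, and that no listed variable measures the conditions themselves.

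A reader might also infer that SR starters are selected for having these conditions and BP starters for lacking them. That is too absolute. The appendix list covers precautions as well as contraindications, and a precaution does not bar use. Intolerance and earlier use of another drug are other routes to SR. Section 9.5.1 cites second-line SR use of 40.4% to 47.9% in published data, so selection after other drugs predates the restriction, though the reasons are not given.

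The reply on size also has force. The magnitudes are assumed, four of five fall below the 10% criterion, and the expected imprecision for infarction in the later stratum far exceeds a shift of 3% to 12%. This limits the weight of the point. It does not justify leaving a named reason for treatment off the candidate list.

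Finally, one might want the variable forced into every SR versus BP model. That would override the plan's own selection rule. A variable that strongly drives drug choice but only weakly affects outcome can cost precision and amplify residual confounding, so the case for forcing it is not made.

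**Conclusion.** The omission is real. It is visible in the protocol's own stated list and does not depend on detail left to a later analysis plan. What is missing is a candidate confounder; bias is not demonstrated, since nothing in the documents shows that these conditions predict the endpoints. The point applies to current SR against current BP, and mainly to SR starters after March 2014 within the stratum from June 2013 onwards. Before then, channelling of this kind is plausible but not stated. The size is unknown: about 3% to 12% inflation under the assumed inputs, with a wider range if stronger associations are assumed. The correction is worth making before data extraction because it is inexpensive and concerns a primary comparison.

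**What to change.** 1. Apply the Appendix 14.3.2 list headed "Contraindications / precautions of use of oral bisphosphonates (and not mentioned in the SR SmPC") to both SR and BP starters, at or before cohort entry, with ulcer or gastro-intestinal bleeding as a separate term.
2. Add it to section 9.3.4 as a baseline candidate covariate, subject to the existing change-in-estimate rule, and name this channelling beside severity in section 9.9.
3. Add to section 9.7.5 one sensitivity analysis of current SR against current BP, restricted in both groups to patients with none of these conditions.

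The cost is small but not nil. Sections 9.3.2 and 9.7.2.2 use the list for SR users only, so it must also be run in the BP starters (around 125,640 expected in section 9.5.2). Several items have no code in IPCI, so the variable will be incomplete there. The restricted analysis will be less precise, most of all in the later period.
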